OMT Trigger Point Protocol Cover Page

Trial Name: Treating Trigger Points: Comparing Muscle Energy Techniques vs. Lidocaine Needling Technique for Pain Control and Quality of Life Measures.

NCT #: NCT05009264

Document Date: April 28, 2022

A comparison of effectiveness of muscle energy technique and dry needling injections on quality of life and pain control in treating trigger points

Introduction

Myofascial pain syndrome is one of the most common musculoskeletal disorders seen in the aging US population ^{1,2}. Its characterized by myofascial trigger points (MTPs) which were first defined by Simons et al. (1999) as hyperirritable nodules in a taut band of skeletal muscle, associated with pain on manual stretching, contraction, or stimulation of the muscle³. Trigger points are further classified into active and latent based on their clinical features ⁴. Active MTPs are characterized by spontaneous pain at rest with referred pain on palpation whereas latent MTPs produce pain on palpation in addition to restriction of range of motion ^{2,4-7}.

Currently, there are a variety of treatment options for MTPs including lidocaine injections, dry needling, osteopathic manipulative treatment, massage therapy, ultrasound therapy etc. There has been a large amount of research investigating the safety and efficacy of dry needling and lidocaine trigger point injection techniques in treating MTPs. The results suggest that dry needling and lidocaine injections were both equally effective in reducing symptoms associated with MTPs as it was the mechanical disruption of the taut fibers due to the needle effect and the depth of adequate penetration that resulted in pain reduction more than the substance actually delivered into the muscle ⁸⁻¹³. Some authors also suggested the importance of a local twitch response (LTR); which is an observable contraction of the taut part of muscle band upon stimulation, during dry needling technique as being pertinent for maximum effectiveness. ^{8,14}However, a recent systemic review found that LTR during dry needling treatment was unnecessary and not required for management of myofascial pain syndrome ¹⁵.

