The study is a prospective cohort study comprised of participants between ages 25-75 presenting to Atlanticare Regional Medical Center interventional pain department and Philadelphia College of Osteopathic Medicine OMM Clinic between April 2021 and May 2021 with trigger point in the upper trapezius muscle. It is expected that approximately 60 patients will be enrolled to produce approximately 50 evaluable subjects.

Inclusion Criteria: The subjects will only be recruited into the study if they have met all the following criteria:

- Ages between 25 and 60 years.
- Previous or current diagnosis of MTrP in the upper trapezius region according to the criteria set by Simons et al.³
- 1 active/latent MTrP in the upper trapezius region

The diagnostic criteria to establish myofascial trigger point is adopted from Travell and Simons³ and include:

1. Presence of palpable taut band in the skeletal muscle
2. Presence of hypersensitive tender spot in the taut band
3. Presence of local twitch response upon stimulation of the taut band
4. Reproduction of referred pain upon palpation
5. Presence of spontaneous referred pain pattern

Exclusion criteria: Any subject that exhibits any of the following criteria will be excluded from the study:

- Pregnancy or immunocompromise
- Fever/infection
- Previous history of whiplash injury
- Previous history of cervical surgery, cervical radiculopathy, or myelopathy
- Severe disc or cervical lesion
- Evidence of cognitive deficit
- Degenerative or inflammatory disease of the cervical spine or shoulder, fibromyalgia, or neuromuscular diseases
- Use of medications (anticoagulants, anti-inflammatory etc.) or illicit drug use (1 week prior to treatment or follow up)
- Received treatment for MPS a month before the study recruitment

All the patients of interest that present to AtlantiCare Regional Medical Center pain clinic and Philadelphia College of Osteopathic Medicine OMM Clinic that meet the relevant inclusion and exclusion criteria will be invited to participate in this study. The subjects will be informed of the purpose of the study and asked for informed consent. If recruited into the study, they will be administered a pre-intervention survey. Subjects will then be managed according to standard of care by their point of care physician. Following the intervention they will be administered a post-intervention survey immediately following the intervention and one-week post.

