The outcome measures, reported pain and quality of life, will be analyzed separately using univariate analyses. The differences between the treatment groups across time periods will be analyzed. A two-factor analysis of variance (ANOVA) will be performed for each dependent variable to determine the

difference between treatment groups at the different time points (before the intervention, immediately after the intervention, and a week post the intervention). A 2 x 3 mixed factor design will be used in order to evaluate the between subjects data (intervention type) across the repeated measures (three time periods).

Study Administration

The primary records of data will be in form of pre- and post- intervention surveys. Each survey will contain a random code to link the patient to the survey data and that list will be kept separate from the surveys. All physical copies of data will be stored primarily at [name] office under lock and key with key access only to them. Data collected through Atlanticare pain clinic will be maintained through one set of copies which will be stored at [name] office under lock and key with key access only to them. Data collected through PCOM will be maintained through one set of copies which will be stored at [name] office under lock and key with key access only to them. Surveys administered through email will be sent through a secure link and all online data will be encrypted with access only to principal investigators and research personal. All data obtained through email will be stored on the principal investigator's computer which is password protected. All data and records generated during this study will be kept confidential in accordance with Institutional policies and HIPAA on subject privacy and the investigator and other site personnel will not use the data and records for any purpose other than conducting the study. The identifiers and other data will be destroyed 5 years after study completion in compliance with the Atlanticare Regional Medical Center data retention policy.

References

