OMT Trigger Point Statistical Analysis Plan Cover Page

Trial Name: Treating Trigger Points: Comparing Muscle Energy Techniques vs. Lidocaine Needling Technique for Pain Control and Quality of Life Measures.

NCT #: NCT05009264

Document Date: August 23, 2022

A comparative study of muscle energy technique and lidocaine injections on treating trigger points

Introduction

Myofascial pain syndrome is one of the most common musculoskeletal disorders seen in the aging US population ^{1,2}. It's characterized by myofascial trigger points (MTPs) which were first defined by Simons et al. (1999) as hyperirritable nodules in a taut band of skeletal muscle, associated with pain on manual stretching, contraction, or stimulation of the muscle³. Trigger points are further classified into active and latent based on their clinical features ⁴. Active MTPs are characterized by spontaneous pain at rest with referred pain on palpation whereas latent MTPs produce pain on palpation in addition to restriction of range of motion ^{2,4-7}. Studies have showed that the upper trapezius is one of the most common muscles affected by myofascial pain syndrome ^{8,9} leading to referred pain manifesting as headaches and stiff neck.

Currently, there are a variety of treatment options for MTPs including lidocaine injections, dry needling, osteopathic manipulative treatment, massage therapy, ultrasound therapy, and pharmacotherapy etc. There have been many studies investigating the safety and efficacy of dry needling and lidocaine trigger point injection techniques in the treatment of MTPs¹⁰⁻¹⁸. It has been demonstrated that both dry needling and lidocaine injections were equally effective in reducing symptoms associated with MTPs; the mechanical disruption of the taut fibers due to the effect of the needle and the depth of adequate penetration resulted in more pain reduction, rather than the substance actually delivered into the muscle ¹⁹⁻²⁴. Some authors also suggested the importance of a local twitch response (LTR); which is an observable contraction of the taut region of the muscle band upon stimulation during dry needling technique, indicating maximum effectiveness of the treatment ^{19,25}. However, a recent systemic review found that LTR during dry needling treatment was unnecessary and not required for management of myofascial pain syndrome ²⁶.

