On the other hand, there has been less research investigating the effects of manual treatment on trigger points. Travell and Simons initially treated trigger points with ischemic compression but later changed their recommendation to applying gentle digital pressure to trigger points ²⁷. A recent study exploring the traction-compression-stretch technique (TTCE) compared to ischemic compression showed some, albeit minor, increased outcome measures (pain pressure threshold) warranting clinical investigation ⁶. Another study compared active release and muscle energy techniques in treating latent trigger points of the upper trapezius and found that both techniques were equally effective in increasing cervical range of motion and decreasing pain and upper trapezius thickness⁷. Other studies have also shown interest in similar osteopathic manipulative techniques such as counterstrain, myofascial release, facilitated positional release and high velocity-low amplitude thrust techniques for treating trigger points^{3,27-29}.

There is no consensus as to which treatment method is superior, leaving the method of treatment up to the discretion of the individual physician, rather than the characteristics of the trigger point itself. Often, determination of treatment method is dependent upon the training received by a physician. There are currently no studies evaluating the efficacy of these various treatment options, specifically osteopathic manipulative treatment vs. trigger point injections. Thus, the intention of the present study was to compare the efficacy of muscle energy techniques vs. lidocaine for the treatment of MTPs in the upper trapezius region.

Study Objective

The primary aim of this study is to compare osteopathic manipulative treatment and lidocaine injection technique for treatment of myofascial trigger points in the upper trapezius region.

Study Design

The study is a prospective cohort study containing of participants between ages 25-65 age range that presented to Atlanticare Regional Medical Center pain management clinic and Philadelphia College of Osteopathic Medicine Osteopathic Clinic between November 2021 and February 2022 with trigger point in the upper trapezius muscle.

Inclusion Criteria: Subjects were recruited into the study if they met all of the following criteria:

- Age between 25 and 65 years.
- Previous or current diagnosis of MTP in the upper trapezius region according to the criteria set by Simons et al.³

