Participants presenting to the Atlanticare Pain Management clinic received a lidocaine injection after dry needling into the location of the MTP by a board-certified pain management physician. First, the upper trapezius MTP was identified and isolated. After application of a coolant to numb the area, the isolated trigger point was penetrated using a 30-gauge needle, to a depth adjusted depending on the patient, into the subcutaneous tissue. The duration of treatment was approximately 1-2 minutes. Once the myofascial tension was relieved, 2 mL of 0.5% lidocaine was injected into the MTP.

After their respective interventions, the patient completed an immediate post-intervention survey, consisting of a 0-10 pain scale. Finally, approximately 7-10 days after the intervention, patients were contacted by telephone to complete the one-week post-intervention survey consisting of a 0-10 pain scale.

Outcome Measures

Pain intensity; measured using a point system; where 0 = no pain and 10 = maximum pain. Although this is a subjective measurement by the patient, we are interested in looking at the difference between pre- and post-intervention pain intensity ratings.

Data Analysis

The data was analyzed using R software. Values of interest include mean, median, standard deviation, normal distribution, confidence intervals etc. Intergroup and intra-group comparisons were conducted using independent t-tests and paired t-tests, respectively. Alpha level is set at 0.05 and p values less than that will be considered statistically significant. A descriptive analysis of the outcome variables was conducted to compare between the intervention groups. The homogeneity of sociodemographic data (age, sex, comorbid conditions) and outcome measures were analyzed using the Fischer test and Pearson chi square test, respectively.

The outcome measures were analyzed separately in both treatment groups. The contrast between the treatment groups was analyzed. A univariate analysis of the difference of the outcome variables at the different time points (before the intervention, immediately after the intervention, and a week post the intervention) were obtained through the student *t*-tests. A multivariate analysis was carried out using multiple logistic regression models with age, sex, and intervention group (Injection = 0, OMM = 1) factored as the independent variables.

Results

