To investigate the treatment effect between groups across time, a mixed design two factor ANOVA was utilized. As expected, due to small sample size, heterogeneity of covariance matrices was detected. This is considered a limitation of the study. Also, since a repeated measures design was implemented across three time periods, Mauchly's test of sphericity was examined and found to be significant ($p = .042$). This indicates that sphericity cannot be assumed, so a Greenhouse-Geisser statistic was computed. A statistically significant interaction effect was detected, $F(1.65, 56) = 3.90, p = .034$. Due to p-value being less than 0.05, we can confidently reject the null hypothesis and accept the alternative hypothesis.

[figure not shown]
Table 1.

Sociodemographic Data	Mean (SD) or Number (%)		P value
	OMM (n = 21)	Lidocaine (n = 10)	
Sex (%), n = 31 (100%)	21 (100)	10 (100)	
Male, n = 7 (22.6%)	5 (23.8)	2 (20)	
Female, n = 24 (77.4%)	16 (76.2)	8 (80)	
Age, y			
Subjects from 20 – 29 y, n = 22 (71%)	21 (100)	1 (10)	
Subjects from 30 – 39 y, n = 1 (3.2%)	0	1 (10)	
Subjects > 60y, n = 8 (25.8%)	0	8 (80)	
Ethnicity			
Caucasian, n = 20 (64.5%)	11 (52.4)	9 (90)	
African American, n = 1 (3.2%)	1 (4.8)	0	
Latino or Hispanic, n = 4 (12.9%)	3 (14.3)	1 (10)	
Asian, n = 6 (19.4%)	6 (28.6)	0	
Pain Intensity			
Pre-intervention	2.76 (1.8)	7 (2.8)	
Post-intervention (immediate)	1.86 (0.9)	6.6 (2.3)	0.026
Post-intervention (one week)	1.81 (2.0)	4 (2.2)	0.062

Table 2.

	Group	Mean	Std. Deviation	N
Pre-intervention Pain	OMM	2.76	1.84	21
	Lidocaine	7.00	3.04	9
	Total	4.03	2.96	30
Post-intervention immediate pain	OMM	1.86	0.96	21
	Lidocaine	6.56	2.45	9
	Total	3.27	2.66	30
Post-intervention 1 week pain	OMM	1.81	2.01	21
	Lidocaine	4.00	2.17	9
	Total	2.47	2.27	30

Figure 1.

Discussion

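### The SAP, written after the data, omits the protocol's mixed ANOVA from its methods, names an undefined and unreported logistic model, and reads the ANOVA interaction (p = .034) as a firm rejection that the design cannot support

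*SAP*

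**What the plan says.** **Protocol, Data Analysis.** One analysis is planned for each outcome: "A 2 x 3 mixed factor design will be used in order to evaluate the between subjects data" across three time points. Alpha is 0.05. No primary time point and no multiplicity rule are given.

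**SAP, Data Analysis.** The mixed ANOVA is not named. The section lists independent t-tests between groups, paired t-tests within groups, and then: "A multivariate analysis was carried out using multiple logistic regression models with age, sex, and intervention group". Pain on a 0-10 scale is the only outcome listed, and no cut-point or event is defined.

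**SAP, Results.** Four within-group t-tests are reported. For the comparison between groups over time, "a mixed design two factor ANOVA was utilized". It gives an interaction of F(1.65, 56) = 3.90, p = .034, after which the text says "we can confidently reject the null hypothesis and accept the alternative hypothesis". No logistic result is reported.

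**SAP, Discussion and Conclusion.** The study is called a pilot. The text says that non-inferiority of OMT was demonstrated and that the two treatments are of similar worth. No margin is given in either document.

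**Dates.** The SAP cover reads "Document Date: August 23, 2022", and its Study Design section puts recruitment "between November 2021 and February 2022". The protocol cover reads "Document Date: April 28, 2022", while its own text places recruitment "between April 2021 and May 2021".

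**The concern.** A reader of the SAP cannot tell which analysis is the reference one. The methods and the results describe different analyses. One named model has neither a defined outcome nor a result. The only formal between-group conclusion comes from a test that the methods section does not mention.

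The larger problem is what that conclusion is taken to mean. A group-by-time interaction tests whether the two groups have parallel mean profiles. Rejecting it says that the profiles differ. It does not say why, and it is not evidence of similarity. These groups were formed by clinic and differ greatly at baseline, so treatment is only one of several explanations. Setting a firm rejection of parallel change beside a claim of comparability or non-inferiority gives the reader two statements that do not fit together, and a small pilot then looks more conclusive than it is.

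**Working it through.** **1. Reproduce the stated p value.** The upper tail of F at 3.90, with both degrees of freedom Greenhouse-Geisser corrected, uses an error df of 1.65 x 28 = 46.2:

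- F(1.65, 46.2): p = 0.0345, which agrees with the stated .034.
- F(1.65, 56), as printed: p = 0.0332. The printed 56 = 2 x 28 is the uncorrected error df.

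The figure stands. It is the interaction of the test that the protocol planned.

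**2. Are the reported within-group t values paired?** The Results label them independent-samples. Unpaired values computed from the reported means and SDs do not match:

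| Comparison | Reported t | Unpaired t |
|---|---|---|
| OMM, pre vs immediate | 2.10 | 1.99 |
| OMM, pre vs one week | 2.68 | 1.60 |
| Lidocaine, pre vs one week | 2.16 | 2.41 |

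The reported p values fit paired df: 20 for OMM (0.049 and 0.014), and 9 and 8 for lidocaine (0.272 and 0.063). With the printed df of 20, the lidocaine values would be 0.256 and 0.043. I therefore assume that the tests are paired.

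**3. One-week change, contrast between groups.** The falls are OMM 2.76 - 1.81 = 0.95 (n = 21) and lidocaine 7.00 - 4.00 = 3.00 (n = 9). The difference is 2.05 points, with the larger fall under lidocaine. The SD of change is mean change x sqrt(n) / t:

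- OMM: 0.95 x sqrt(21) / 2.68 = 1.62, SE 0.354.
- Lidocaine: 3.00 x 3 / 2.16 = 4.17, SE 1.389.

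Pooled:
- SD = sqrt[(20 x 1.62² + 8 x 4.17²) / 28] = 2.62
- SE = 2.62 x sqrt(1/21 + 1/9) = 1.04
- t = 1.97 on 28 df, p = 0.059, 95% CI -0.09 to 4.19

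Welch:
- SE = sqrt(0.354² + 1.389²) = 1.43
- t = 1.43 on 9.1 df, p = 0.19, 95% CI -1.19 to 5.29

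**4. Another independent t-test that the SAP wording allows.** On the raw one-week scores (Table 2: 1.81, SD 2.01, n = 21; 4.00, SD 2.17, n = 9), p = 0.012 pooled and 0.021 Welch, with the lower score under OMM. The gap there is 2.19 points, against 7.00 - 2.76 = 4.24 at baseline. Raw score and change point in opposite directions, and the SAP does not say which is meant.

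**5. Comparability of the groups.**

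- Baseline pain 2.76 vs 7.00 (Table 2): p = 0.00006 pooled, 0.003 Welch.
- Age 20-29 (Table 1): 21 of 21 OMM and 1 of 10 lidocaine; above that band, 0 and 9. Fisher exact p = 5e-7, although the Results report no significant sociodemographic difference.
- Age and group in one model: variance inflation factor about 4.7 if the bands are valued at 25, 35 and 62.5 years (assumed), and about 7.1 with age split at 30.

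**6. The logistic model.** It cannot be recomputed, because no event is defined. With 31 patients the rarer category holds at most 15, so three covariates leave at most 15 / 3 = 5 events per variable at any cut-point.

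**The case against.** The strongest reply is that the Results used the protocol's own analysis. A reader might infer from the SAP's late date and its change of methods that the ANOVA was picked because it was significant. The documents do not support this: the protocol names exactly that ANOVA, and the p value reproduces. Nor was the rejected p value produced by the logistic model, for which no result exists.

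A reader might also infer that no analysis was fixed before the data. That is unresolved. The protocol's text is prospective and gives an April to May 2021 window, which favours genuine planning. Its cover date falls after the recruitment window stated in the SAP, so the dates do not settle it either way.

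It would also be too strong to say that the logistic model could never be fitted, or that any age adjustment rests on one lidocaine patient. The first is a missing event definition. The second holds only if age enters in bands, which the SAP does not say. What the figures show is severe collinearity and reliance on extrapolation.

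Counting the four t-tests and the interaction as five tests would give a family-wise error of 1 - 0.95^5 = 22.6% if they were independent. The four are within-group tests of other hypotheses, however, so that is not the error rate of the interaction.

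Finally, the SAP does call the study a pilot. It admits heterogeneous covariance matrices, and it lists the small sample, the age difference and the baseline pain gap as limitations. These caveats are fair and count in its favour, but they contradict the rejection sentence and do not repair it.

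**Conclusion.** The point holds as a mismatch between methods and results, together with an over-reading of one p value. The SAP methods omit the analysis behind the only formal between-group conclusion and name a logistic model with no event and no result. No null hypothesis, primary time point or multiplicity rule is stated.

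The interaction (p = .034) says that the groups changed differently: one-week falls of 0.95 and 3.00 points. With 30 analysed patients allocated by clinic, a baseline gap of 4.24 points and almost no overlap in age, that difference cannot be assigned to treatment. It does not support comparability, and non-inferiority has no margin to be judged against.

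The conclusion is also sensitive to the analysis. The one-week difference in change is 2.05 points, with a Welch 95% CI of -1.19 to 5.29 (p = 0.19) and a pooled p of 0.059. These figures rest on the assumption that the reported t values are paired, on rounded summaries, and on 21 and 9 patients. Patient-level data would replace them. That a favourable test was selected is not part of this finding.

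**What to change.** In the SAP:

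1. Name the protocol's 2 x 3 mixed ANOVA in Data Analysis as the reference analysis.
2. Delete the logistic model. If it was run, disclose its event definition and result, marked post hoc.
3. If an adjusted model is wanted, use a linear model for the one-week pain score with baseline pain as covariate. Label it a sensitivity analysis that does not remove confounding by clinic or age. Baseline should not be added as a covariate to the mixed ANOVA, where it is already one of the three outcome time points.
4. State that the SAP was written after data collection and label all p values exploratory.
5. Delete the rejection sentence. Report the between-group difference in change with a 95% CI that allows unequal variances, and withdraw the comparability and non-inferiority statements as conclusions from this test.

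The cost is changes of wording and one rerun on existing data. The downside is that the significance claim is lost.

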The study was completed at two primary locations. There were a total of 10 eligible participants from the lidocaine treatment group and 21 eligible participants from the OMM treatment group enrolled after screening for the inclusion and exclusion criteria. 1 subject from the lidocaine treatment group was lost during follow-up at one week post intervention and thus excluded from the per protocol analysis of the study. The remaining participants' data were analyzed in SPSS 26. No significant difference was found between the two groups in regard to sociodemographic data (Table 1). At baseline, the OMM group had a mean pain intensity level of 2.76 (SD 1.8) while the lidocaine treatment group had a mean pain intensity level of 7 (SD 2.8). Descriptive statistics of pain intensity between the two groups demonstrate considerable variance (Table 2).

Within the OMM group, an independent samples t-test found a statistically significant difference between the pre-intervention and immediate post-intervention pain levels, $t(20) = 2.10, p = .048$. The mean pre-intervention pain level ($M = 2.76, SD = 1.84$) was significantly higher than the immediate post intervention pain level ($M = 1.86, SD = 0.96$). An independent samples t-test found a statistically significant difference between pre-intervention and one-week post-intervention pain levels, $t(20) = 2.68 p = .014$. The mean pre-intervention level of pain ($M = 2.76, SD = 1.84$) was significantly higher than one-week post-intervention ($M = 1.81, SD = 2.01$).

Within the lidocaine group, an independent samples t-test did not demonstrate a statistically significant difference between pre-intervention and immediate post-intervention pain levels, $t(20) = 1.17, p = 0.27$. The mean pain level pre-intervention ($M = 7, SD = 2.87$) was higher than immediately post-intervention ($M = 6.60, SD = 2.32$). When evaluating the difference in level of pain from pre-intervention to one-week post-intervention, an independent samples t-test was not statistically significant, $t(20) = 2.16 p = .062$. The mean level of pain pre-intervention ($M = 7, SD = 2.87$) was higher than one-week post-intervention ($M = 4, SD = 2.18$). Pain intensity between the two groups are also demonstrated graphically in Figure 1, with time point one corresponding to pre-intervention, two corresponding to immediately post-intervention and three corresponding to 1 week post intervention.

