We specifically note that this is a suitable treatment modality for all physicians, both osteopathic and allopathic, as we merge our skill sets over time in a unified manner. As mentioned, the training of a physician usually dictates the management decisions regarding MTP treatment. This study was conducted in a post graduate training institution that has multiple specialty programs with osteopathic recognition. In the single accreditation system, collaborating with allopathic physicians and exposing allopathic residents to osteopathic treatment options was viewed an advancement for patient centered care and osteopathic awareness. As more allopathic physicians expand their skill sets and complete OMT courses, demonstrating the efficacy of a common treatment modality compared to OMT will assist with treatment choice. Comparable efficacy of both options will help patients choose the option that best meets their needs and physicians choose the option that best augments their skill set.

Being a pilot study, we anticipated a considerable degree of limitations throughout the study. Limitations include but are not limited to low sample size, majority female participants, and substantial difference in mean age between the two groups. Additionally, the OMT intervention group had a significantly lower mean pre-intervention pain level compared to the lidocaine group which made it difficult to do a true comparative analysis between groups. However, as a pilot study, demonstration of OMT non-inferiority compared to a standard treatment modality, creates a stepping stone for future research to investigate the comparative efficacy of OMT on a larger scale and we therefore anticipate future trials with larger number of participants to demonstrate more significant data and results.

Conclusion

Based on our study, OMT has comparable value with lidocaine injection technique as a treatment modality for active TrPs in the upper trapezius region. Both techniques demonstrate considerable decrease in pain intensity from baseline and thus it allows for increased collaboration between osteopathic and allopathic practitioners to promote patient centered care.

References

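### The SAP's only covariate-adjusted model leaves out baseline pain, and the direction of the one-week comparison depends on how baseline pain is handled

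*SAP*

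**What the plan says.** - **SAP, Data Analysis.** Between-group and within-group comparisons are by t-test. The only model with covariates is "multiple logistic regression models with age, sex, and intervention group (Injection = 0, OMM = 1) factored as the independent variables". No binary outcome is defined for the 0-10 pain score, and Results reports nothing from this model.
- **SAP, Outcome Measures.** The stated interest is pre/post change: "we are interested in looking at the difference between pre- and post-intervention pain intensity ratings".
- **SAP, Results, and Protocol, Data Analysis.** Both use a mixed two-factor ANOVA of group by three time points, with the pre-intervention score as the first time level. Neither makes it a covariate.
- **SAP, Discussion.** The limitations paragraph says that the OMM arm had a "significantly lower mean pre-intervention pain level compared to the lidocaine group which made it difficult to do a true comparative analysis between groups". It also lists a "substantial difference in mean age between the two groups". The Discussion nevertheless speaks of equal efficacy and of demonstrated non-inferiority, and says that the one-week reduction was larger with lidocaine. The Conclusion calls the two treatments comparable in value.

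**The concern.** Baseline pain was collected at enrolment and differs between arms by 4.24 points on a 0-10 scale. The covariates chosen instead do little. Sex is already balanced (23.8% v 20% male, SAP Table 1). Age nearly coincides with group: all 21 OMM patients but only 1 of 10 lidocaine patients are aged 20-29.

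Comparing change scores, as the group-by-time interaction does, assumes that each extra point of baseline pain carries one extra point into the follow-up score. If the true slope is lower, the change score over-corrects in favour of the arm that started higher; if no correction is made, the raw score favours the arm that started lower. With a gap this large, that choice can decide which arm looks better, and with it whether the Discussion's comparative statements can stand.

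**Working it through.** **Inputs.** SAP Table 2: OMM n=21, baseline 2.76 (SD 1.84), one week 1.81 (2.01); lidocaine n=9, baseline 7.00 (3.04), one week 4.00 (2.17; the Results text gives 2.18). SAP Results, baseline to one week: OMM t=2.68, p=.014; lidocaine t=2.16, p=.062.

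**1. Reproduce the printed tests.** As paired tests, t=2.68 on 20 df gives p=.014, and t=2.16 on 8 df gives p=.063, which is .062 within the rounding of t. The 20 df printed for lidocaine would give .043. Independent-samples tests on the printed SDs give .118 and .028. The p-values therefore come from paired tests, although the text labels them independent.

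**2. Recover the sums.** Pain scores are taken as whole numbers.
- OMM: sums 58 (baseline) and 38 (one week); sums of squares 228 and 150; sum of squared differences 72.
- Lidocaine: sums 63 and 36; sums of squares 515 and 182; sum of squared differences 219.

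These return t=2.68 (p=.014) and t=2.17 (p=.062). They imply one-week SDs of 2.015 and 2.179, so Table 2's 2.01 and 2.17 must be truncated rather than rounded.

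**3. Within-arm sums about the mean.** With x = baseline and y = one week, Sxy = (Sxx + Syy - Sdd)/2, where Sdd is the sum of squares of the differences about their mean.
- OMM: Sxx 67.81, Syy 81.24, Sdd 72 - 20²/21 = 52.95, so Sxy = 48.05.
- Lidocaine: Sxx 74, Syy 38, Sdd 219 - 27²/9 = 138, so Sxy = -13.

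**4. Three one-week comparisons** (OMM minus lidocaine; negative favours OMM; pooled variance).
- Raw: 1.81 - 4.00 = -2.19. SE = √[(81.24+38)/28 × (1/21+1/9)] = 0.822; 95% CI -3.87 to -0.51.
- Change: -0.95 - (-3.00) = +2.05. SE = √[(52.95+138)/28 × (1/21+1/9)] = 1.040; CI -0.08 to 4.18, p=.059.
- Common-slope adjusted: slope = (48.05-13)/(67.81+74) = 0.247 (CI -0.10 to 0.60). Difference = -2.19 - 0.247×(-4.24) = -1.14. SE 1.081 on 27 df; CI -3.36 to 1.08, p=.30.

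The sign turns only if the slope exceeds 2.19/4.24 = 0.52. The change score sets it at 1.

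**5. Sensitivity to rounding.** Working from the printed rounded values instead of the recovered sums gives an adjusted difference of -1.17 (CI -3.38 to 1.05, p=.29).

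**6. Is one slope adequate?** The slopes are 48.05/67.81 = 0.71 (OMM) and -13/74 = -0.18 (lidocaine). Residual sums of squares are 110.58 with a common slope and 82.91 with separate slopes, so F(1,26) = (110.58-82.91)/(82.91/26) = 8.68, p=.007. With separate slopes and pooled variance:

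| Baseline pain | Difference | 95% CI |
|---|---|---|
| 2.76 | -2.9 | -5.3 to -0.6 |
| 6 | -0.1 | -2.2 to 2.0 |
| 7 | +0.8 | -1.6 to 3.2 |

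**7. Immediate score, same method.** The change difference is -0.46 (p=.52) and the common-slope adjusted difference is -2.90 (CI -4.25 to -1.54), again with unlike slopes (0.06 v 0.76). The sign agrees here, but the size does not.

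**The case against.** **Baseline is not ignored.** This stands. The SAP defines its interest as pre/post change, and the group-by-time interaction compares change between arms. In non-randomised arms, change score against baseline adjustment is a choice of what to estimate, and neither is causal. What remains is that only one handling of baseline was used, without justification, and the fitted slope of about 0.25 is far from the slope of 1 that it implies.

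**The logistic model drives no printed conclusion.** Also true. The Discussion rests on the t-tests and the ANOVA, and its statement that lidocaine had the larger one-week fall is plain subtraction (3.00 v 0.95). Changing the covariates of an unreported model would alter no printed number. The point is that the only adjustment offered cannot address the imbalance that the SAP names.

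**The adjusted figure is itself fragile.** It is. The lidocaine slope rests on nine patients (95% CI about -0.80 to 0.45), and the unequal slopes undercut the common-slope estimate. Allowing unequal variances, the interaction p is .016 and the interval at baseline 2.76 widens to -6.1 to 0.3, which includes zero.

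**The SAP already concedes the difficulty.** In part: its limitations paragraph does so, and the Discussion says that neither technique was clearly superior. The claims of equality and non-inferiority remain alongside that concession.

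**Conclusion.** The point holds as a dependence on method. The one covariate-adjusted model omits the large imbalance that the SAP itself names, and the one-week estimate runs from -2.19 through -1.14 to +2.05 according to how baseline pain is treated. Both one-week estimates that use baseline, the change score and the common-slope adjustment, have intervals that include zero. No margin was set, so equal efficacy and non-inferiority are not shown.

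Two stronger readings should be resisted. A reader might infer that the result changes direction once baseline is taken into account. It does not: adjustment roughly halves the raw difference and keeps its sign, and the reading it reverses is the change score, which already uses baseline. A reader might also take -1.14 as the true effect. The unequal slopes, nine lidocaine completers, allocation by clinic and near-complete separation by age rule that out.

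The figures assume paired t values, whole-number scores and truncated SDs in Table 2. The pairing assumption matters most: a baseline-to-one-week correlation in the lidocaine arm of about 0.45 or more, instead of the derived -0.26, would turn the adjusted sign as well.

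**What to change.** **SAP, Data Analysis.** Keep the record of what was done and add, labelled post hoc, a linear model of one-week pain on group and centred baseline pain, and the same for immediate pain. Fit each with and without the group-by-baseline term. Report group differences with confidence intervals at baseline scores observed in both arms, beside the unadjusted change difference. The documents print no ranges, so the overlap must be read from the patient data. Robust standard errors are optional. Do not rely on the logistic model; show age descriptively, as confounding with clinic that remains.

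**SAP, Discussion and Conclusion.** Replace the wording of equal efficacy, demonstrated non-inferiority and comparable value. Say that the comparison depends on how baseline is handled, that no margin was set, and that no estimate is causal because treatment followed clinic. Take the statement on the intervals from the re-run; on the printed data, the one-week change-score and common-slope intervals both include zero.

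**Cost.** One re-run on data already collected and revised text. The price is a less favourable, inconclusive comparison.
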